Despite awareness in the celiac community of the potential for pancreatic exocrine insufficiency as a complication of celiac disease, there have been few prospective studies of pancreatic enzyme replacement in celiac disease and no studies to date that have taken place in the United States. As the population with celiac disease has expanded rapidly in recent years, 30 the potential for adjunctive therapies for celiac disease has become more apparent. In this study, we propose to conduct a rigorous prospective study of the utility of pancreatic enzyme replacement in celiac disease and assess the ability of fecal elastase levels to predict response to therapy.

Our goal is to provide adequate supplementation over the 10 day treatment period so as to maximize the opportunity for an evident therapeutic effect if indeed pancreatic enzyme insufficiency is contributing to the subjects' symptoms.

B3. DESCRIPTION OF RESEARCH PROTOCOL

A. Study Design – Overview, Methods, Procedures

Overview

This is a single-center investigator initiated phase IV trial to examine the efficacy of pancreatic enzyme supplementation in individuals with celiac disease who suffer persistent symptoms despite a gluten free diet.

Hypothesis

Pancreatic enzyme supplementation will improve symptoms in individuals with celiac disease who suffer persistent symptoms despite a gluten free diet.

Specific Aims:

Specific Aim 1: Evaluate the efficacy of pancreatic enzyme supplementation for reduction of gastrointestinal symptoms in patients with celiac disease on a gluten free diet.

Specific Aim 2: Assess the ability of fecal elastase levels to predict response to pancreatic enzyme supplementation in patients with celiac disease on a gluten free diet.

Primary Objective(s)/End Point(s):

The primary endpoint for Specific Aim 1 will be the average per individual subject on-treatment score in the Celiac Disease Gastrointestinal Symptom Rating Scale (CeD GSRS) domains of Diarrhea, Indigestion, and Abdominal pain comparing active treatment to placebo (i.e. a paired comparison of CeD GSRRS on treatment versus on placebo for each subject). The outcome measures used in the study and in particular the CeD GSRS have been employed previously by the investigators in their published studies. 31-33

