As a primary endpoint for Specific Aim 2, baseline fecal elastase measurement will be correlated to the average difference in on-treatment score in the CeD GSRS [active versus placebo].

Secondary Objective(s)/End Point(s):

- (1) Assessment of response to pancreatic enzyme supplementation in patients with celiac disease and either normal or low baseline fecal elastase levels.
- (2) Improvement in Celiac Symptom Index (CSI) with active treatment vs. placebo.
- (3) Reduction in number of total stools and loose stools (defined as a Bristol Score of 6-7) per week with active treatment vs. placebo.

Experimental Design & Number and Description of Each Treatment Arm/Group:

We propose a randomized, double blind, placebo-controlled, crossover trial of 40 participants overall. Participants would have a 7 day placebo run in period for documentation of symptoms at baseline (study phase 1), followed by a 10 day treatment/placebo period (study phase 2), after which there would be another 7 day wash out period (study phase 3) and a final 10 day cross over (study phase 4) resulting in a total study duration of 34 days.

Participants will be recruited from the Celiac Center at Beth Israel Deaconess Medical Center which currently has over 1900 registered patients with biopsy proven celiac disease. Patients will be enrolled in the out-patient clinic and though targeted mailings and advertisements. Males and Females over the age of 18 with biopsy-proven celiac disease and persisting symptoms despite adherence to a strict gluten free diet will be targeted 19.

Study visits would occur at screening (Visit 1), beginning of the third study phase (day 17-21, Visit 2) and study conclusion (day 35-40, Visit 3). Participants will regularly complete symptom surveys (Celiac Dietary Adherence Test [CDAT], to be administered at baseline; the CSI, to be administered daily; CeD-GSRS & a modified CSI, which are to be administered at the end of each study phase), a daily stool log (frequency and consistency), and a daily medication log. Participants will be contacted every 3 (±1) days after enrollment for safety and compliance assessments (e.g. medication, symptoms surveys, and stool log review).

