Study visits will occur at screening (Visit 1), beginning of the second study phase (day 14-21, Visit 2) and study conclusion (day 35-40, Visit 3). Each of these visits will include medical history review by study personnel, a physical exam performed by a licensed study physician, and the collection of vital signs. Visit 1 will include a dietetic assessment to be completed with a Celiac Center dietician. This dietetic assessment will occur either in-person at Visit 1 following the consent or following Visit 1 over the phone prior to the start of the study medication. The purpose of this dietetic assessment is to (1) evaluate for recent gluten exposure and obvious other food intolerances (e.g. moderate lactose intolerance, FODMAP intolerance), and (2) educate the subject regarding the diet they should follow while on the study.

At Visit 1 participants will be asked to complete the CeD-GSRS, CSI, and CDAT questionnaires. Following Visit 1, participants will be asked to complete the CSI once each day for the duration of the study period. Participants will additionally complete the CeD-GSRS and a specialized CSI that includes a question regarding potential gluten exposure at the end of each study phase, i.e at days 7, 17, 24, and 34 (please see the protocol schema on page 14 below for a depiction of the study phases).

If participants do not attend Visit 2 until after study day 17 they will be instructed to stop taking study medication, including omeprazole if prescribed for the study, until they attend Visit 2 and can receive the placebo washout.

Participants will additionally complete a daily medication log to record when they take the study medication and a daily paper stool log to record bowel movement frequency and consistency.

Participants will be contacted every 3 (±1) days after enrollment for safety and compliance assessments (e.g. medication, symptoms survey, and stool log review).

Laboratory Assessments:

Safety outcomes will be assessed at visit 1 (screening) and 3 (study conclusion) and will include:

- Celiac serologies (IgA tTG and IgA/IgG DGP)
- Complete blood count (CBC)
- Basic metabolic panel (BMP)

Fecal elastase will additionally be assessed at Visit 1. Stool sampling for fecal elastase testing will occur at Visit 1 when possible or a stool sample will be returned at Visit 2.

Female subjects will be asked to provide a urine sample at Visit 1 for β-HcG pregnancy testing.

Safety Evaluations:

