Efficacy analyses will include all patients receiving ≥1 dose of study drug during double-blind treatment and with ≥1 post-baseline assessment (Modified Intent-to-Treat [MITT] population). Baseline score will be considered the last non-missing observation before the first dose of pancreatic enzyme or placebo. The primary endpoint is the difference in mean CeD-GSRS score on treatment vs. placebo. Mean score for each participant will be generated by averaging the daily patient reported outcome (CeD-GSRS and CSI) scores across the study periods, such that there will be a single mean score per participant for the run-in phase and each treatment phase. The mean intrasubject score will then be averaged across the entire cohort for the relevant study phase.

We will use standard two-treatment cross over study analysis in which participant scores during drug treatment (GSRS_{rx}) for the primary outcome are compared to participant scores on placebo (GSRS_{pcb}). Assuming the data are normally distributed, if pancreatic enzyme supplementation is effective we would expect GSRS_{rx} < GSRS_{pcb}. The study as describe above is powered so that we will reach statistical significance if GSRS_{pcb} - GSRS_{rx} >0.4 using Student's paired t-test p<0.05.

Sensitivity analyses will be conducted using Mixed Model for Repeated Measures (MMRM). MMRM analyses will include treatment and study week as main effects, gender, baseline CeD-GSRS score as covariates, and weekly CeD-GSRS scores as repeated measures. Should data be non-normal, we will transform results into categorical data by calculating the proportion of patients with a >30% reduction in CeD-GSRS score on treatment and on placebo compared to their individual scores at baseline. If treatment is effective, we would expect a significantly greater proportion of patients to have a minimally clinically significant difference in GSRS score on treatment compared to placebo which can be evaluated using the Fishers Exact Test.

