- 3. Patients with a pork allergy or who are unwilling to consume pork products.
- 4. English proficiency unsuitable for completion of surveys.
- 5. Known severe pancreatic disease.
- 6. Known history of prior cancer (except squamous or basal cell skin cancer).
- 7. Patients with lactose intolerance who are unable to tolerate a minimum of 1oz (2 tablespoons) of whole milk per day.
- 8. Clinically significant abnormality in safety lab values (i.e. CBC and BMP) at screening that may impact subject safety or the scientific integrity of the study.
- 9. Other known active GI condition including but not limited to inflammatory bowel disease, small intestine bacterial overgrowth, and obvious FODMAP intolerance.
- 10. History of all major gastrointestinal surgery other than appendectomy or cholecystectomy.
- 11. Comorbid condition that in the opinion of the investigator would interfere with the subject's participation in the study or would confound the results of the study.

B4. POSSIBLE BENEFITS

If effective, pancreatic enzyme supplementation may improve symptoms in individuals with celiac disease who suffer persistent symptoms despite a gluten free diet.

B5. POSSIBLE RISKS AND ANALYSIS OF RISK/BENEFIT RATIO

Possible risks include those associated with the study drug and blood draw.

Viokace

Common Adverse Effects:

- Gastrointestinal: Diarrhea (up to 10%), Indigestion (10%)
- Respiratory: Cough (6% to 10%)

Serious/Rare Side Effects:

- Gastrointestinal: Distal intestinal obstruction syndrome, Fibrosing colonopathy (Rare), Stricture of colon (Rare)
- Immunologic: Anaphylaxis, Hypersensitivity reaction

Other: Recurrent tumor, Carcinoma

There is additional theoretical risk of transmission of viral disease from Viokace to the study participant as Viokace is sourced from porcine pancreatic tissue. This risk has been reduced by testing for and inactivating certain viruses during manufacturing. No cases of transmission of an infectious illness associated with use of porcine pancreatic products have been reported to-date.

Omeprazole

Common Adverse Effects

- Gastrointestinal: Abdominal pain (5.2%), Diarrhea (3.7%), Flatulence (2.7%), Nausea (4%), Vomiting (3.2%)
- Neurologic: Headache (6.9%)

Serious/Rare Side Effects:

- Dermatologic: Erythema multiforme (rare), Stevens-Johnson syndrome (rare), Toxic epidermal necrolysis (rare)
- Endocrine metabolic: Hypomagnesemia (rare)
- Gastrointestinal: Clostridium difficile diarrhea, Pancreatitis (rare)

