
[figure not shown]

(Screening)

Visit 1

Medical Hx

Protocol Appendix A

Total duration of study medication administration = 34 days
Omeprazole co-prescribed for entire duration of study
Phone Contacts every 3 +/- 1 days

Daily stool consistency log & Daily medication log Daily CSI questionnaire & Weekly CSI and CeD-GSRS Questionnaires

*Phase 1 will begin once the subject's safety and celiac serologies have returned and been evaluated by a study physician. At that point the subject will be instructed to begin taking the study medication and to begin completing the daily and weekly questionnaires.

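### A participant who stops mid-phase has no assured on-treatment CeD-GSRS: the dated schedule takes one per treatment phase and none at stopping, and the analysis text assumes a different frequency

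*Combined protocol and SAP*

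**What the plan says.** Five places in the combined protocol and SAP set the timing of the CeD-GSRS, and they do not agree.

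- B3.A, Number and Timing of Visits/Evaluations: "at the end of each study phase, i.e at days 7, 17, 24, and 34", in addition to Visit 1. Only the CSI is daily here.
- B3.A, Experimental Design: "CeD-GSRS & a modified CSI, which are to be administered at the end of each study phase", which agrees.
- B3.B, Data Analysis, primary score: formed by "averaging the daily patient reported outcome (CeD-GSRS and CSI) scores across the study periods".
- B3.B, Data Analysis, mixed-model sensitivity analysis: "weekly CeD-GSRS scores as repeated measures".
- Appendix A: "Daily CSI questionnaire & Weekly CSI and CeD-GSRS Questionnaires".

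The primary endpoint is a within-subject comparison of the "domains of Diarrhea, Indigestion, and Abdominal pain comparing active treatment to placebo", tested with a paired t-test. The modified intent-to-treat set admits anyone with one dose and one post-baseline assessment. No rule says how someone scored in only one treatment phase enters a paired test, and there is no imputation rule. The plan sets no CeD-GSRS at early stopping and does not say whether questionnaires continue once capsules stop.

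On contacts, B3.A states: "Participants will be contacted every 3 (±1) days after enrollment for safety and compliance assessments". These calls are not tied to days 7, 17, 24 or 34. Visit 2 falls on day 17-21 in one place and 14-21 in another, and Visit 3 on day 35-40, so the forms due on days 7, 24 and 34 coincide with no visit. Section B5 lists diarrhea (up to 10%) and indigestion (10%) as common effects of the active drug.

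**The concern.** On the dated schedule, the whole primary contribution of a treatment phase rests on one form on its last day. Someone who leaves on days 8-16 or 25-33 has been exposed but may never be asked for that form. A paired t-test needs both phases, so one missing form costs the pair.

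Two of the three primary domains are also listed adverse effects of the enzyme. If some participants stop enzyme because these symptoms worsen, the missing scores would be the unfavorable ones, and the comparison among those left would flatter the drug. Recruiting until 30 participants have completed the treatment phases protects the number of pairs but not against this selection. An uncollected score cannot be recovered at the analysis stage.

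A simpler loss affects completers. A form missed on day 7, 24 or 34 may be noticed only at a call up to 4 days later, when the participant is in the next phase or off treatment.

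**Working it through.** **1. The schedule under each reading.** Treatment phases are days 8-17 and 25-34. For a participant who stops *assessments* mid-phase:

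- Phase-end timing: no score for that phase.
- Weekly timing counted from Day 1: days 14 and 28 fall inside the phases. Leaving on days 8-13 or 25-27 still gives no score; leaving after day 14 or 28 gives one.
- Daily timing: nearly everyone has a partial-phase mean. No data-collection section schedules a daily CeD-GSRS; only the analysis text assumes one.

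**2. The plan's own sample size (B3.B).** Inputs: difference 0.4, SD 0.55, alpha 0.05 (two-sided assumed), 80% power, 10% drop-out, 32 participants. The plan does not say what the 0.55 measures.

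- As within-subject SD: SD of differences = 0.55 × √2 = 0.778. Normal approximation: ((1.960 + 0.842) × 0.778/0.4)² = 29.7, so 30 pairs, and 30/0.9 gives 34. By noncentral t, 32 evaluable pairs give 80.4% power. The stated 32 is reproduced exactly before drop-out, and within 2 after it.
- As SD of differences: 15 pairs (normal) or 17 (t), or 17 to 19 after drop-out. This is well short of 32, so the first reading fits better, but both are carried forward.

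**3. Cost of missed pairs.** Paired t, noncentrality = 0.4 × √n / SD of differences, n − 1 degrees of freedom, two-sided 0.05:

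| SD of differences | 30 pairs | 27 pairs |
|---|---|---|
| 0.778 | 77.7% | 73.0% |
| 0.55 | 97.1% | 95.3% |

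**4. Illustration of selective loss.** Everything here except the 0.4 target and the 30 completers is assumed. Suppose 30 completers have a mean benefit (placebo minus active) of 0.40, and k exposed participants stop on active with benefit e. The mean over all is (30 × 0.40 + k × e)/(30 + k):

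| k | e = 0 | e = -0.8 |
|---|---|---|
| 1 | 12.0/31 = 0.387 | 11.2/31 = 0.361 |
| 2 | 12.0/32 = 0.375 | 10.4/32 = 0.325 |
| 3 | 12.0/33 = 0.364 | 9.6/33 = 0.291 |

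The completers-only result of 0.40 would then exceed the mean over all by 0.01 to 0.11. Three stoppers are 3/33 = 9.1%, within the plan's 10%. Four would be 4/34 = 11.8%, outside it.

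Putting all three in the active phase is the unfavorable extreme. Spread evenly over 34 days, 3 × 10/34 = 0.9, about one, would fall there, and the excess is 0.01 to 0.04 (first row).

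**5. Call days.** Days 3, 7, 10, 14, 17, 20, 24, 27, 31 and 34 have gaps of 4, 3, 4, 3, 3, 4, 3, 4 and 3 days. All meet the existing 3 (±1)-day rule, and every phase end has a call.

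**The case against.** A reader might infer more than the documents support, in four ways.

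- *That a stopper has no primary score.* The schedule attaches the form to a study day, not to dosing. Someone who stops capsules on day 12 could still complete day 17, and on a daily or weekly reading might already have a score. What stands is that nothing assures a score, and a day-17 form completed days after stopping may describe symptoms off the drug.
- *That stoppers contribute nothing.* The analysis set keeps them, the mixed model can use one-phase data, and the daily CSI and stool log record symptoms before stopping. But the mixed model is only a sensitivity analysis, relies on missing-at-random, and expects weekly scores that the dated schedule does not supply. The CSI and stool log are not the primary measure.
- *That the result is biased toward enzyme.* B5 gives event frequencies, not discontinuation rates. Stopping on placebo for lack of relief would push the other way. Omeprazole (abdominal pain 5.2%, diarrhea 3.7%) is co-prescribed throughout, and the capsule load, up to 15 × 2 = 30 a day, is matched in every phase. Either could cause stopping on active or placebo.
- *That a questionnaire at stopping restores the primary test.* A participant who stops in phase 2 and leaves has no phase 4 score, so there is still no pair.

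All four limits stand. They restrict the point to an unprotected data-collection step; they do not remove it.

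**Conclusion.** The point holds in limited form. The dated schedule gives one CeD-GSRS per treatment phase, none at early stopping and no contact on the phase-end day, and the analysis section and Appendix A assume other frequencies. A mid-phase stopper has no assured on-treatment primary score and can drop out of the paired t-test. Because the drug's listed effects overlap the primary domains, such loss could be informative and could favor enzyme.

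The documents establish neither that this would happen nor how large it would be. The 0.01 to 0.11 excess rests on assumed numbers of stoppers and assumed scores; its upper end, about a quarter of the 0.4-point target (0.109/0.4 = 27%), needs all three stoppers to be on active and 0.8 points worse there than on placebo. The power loss is about 5 percentage points (78% to 73%) if 0.55 is the within-subject SD, and about 2 (97% to 95%) if it is the SD of differences. The change is still worth making, because it is cheap and a score not taken is lost.

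**What to change.** 1. Reconcile the CeD-GSRS frequency across B3.A (Experimental Design; Number and Timing of Visits/Evaluations), B3.B Data Analysis and Appendix A, including the input to the mixed model.
2. In Number and Timing of Visits/Evaluations, add: *A participant who stops study medication during phase 2 or 4 completes the CeD-GSRS and modified CSI within 1 day of stopping, or at the next contact if stopping is first learned then, referring to the days on medication, and is still asked to complete the remaining phase-end questionnaires.*
3. Place the existing calls so that one falls on the last day of each phase, for example on the call days listed in the working. Shift the days for phases 3 and 4 when Visit 2 comes after day 17, because study medication is then paused until that visit.
4. Keep the paired t-test for participants with both scores, and report alongside it the planned mixed model including one-phase participants.

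The cost is one sentence, a call calendar and one existing questionnaire for the few who stop. It adds no visit or routine call and changes no dose or rule for stopping treatment. Two limits remain: an early stopper's score reflects fewer than 10 days of treatment, and the mixed model relies on missing-at-random for the absent phase.

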Safety evaluations will occur at all study visits and contacts through interview with study personnel, and/or physical examination, and/or symptom monitoring via the weekly surveys. Safety outcomes will include celiac serologies (IgA tTG and IgA/IgG DGP), CBC, and BMP on screening and study conclusion.

Adverse events (AEs) will be assessed at study visits and contacts. Serious adverse events (SAEs) will be defined as those that: result in death; are an immediate threat to life; require inpatient hospitalization, or prolongation of existing hospitalization; result in persistent or significant disability/incapacity; and/or are a congenital anomaly or birth defect.

For all AEs we will provide an assessment of causal relationship to the IP. Causal relationship will be assessed by answering the following question: Is there a reasonable possibility the IP caused the event? The answer to this question is "yes" if there is evidence to suggest a casual relationship between the drug and the adverse event (i.e. there is a reasonable temporal relationship, and/or the events are unlikely to be attributable to underlying disease, other drugs, or

other factors). Dechallenge and/or rechallenge (if available) is positive. The answer to this question is "no" if the relationship is unlikely or nonexistent (i.e. there is no reasonable temporal relationship and/or the events are likely to be manifestations of underlying diseases, or commonly occur in the study population independent of drug exposure or other drugs/factors provide plausible explanations for the events), or the patient did not take the investigational product.

The Principal Investigator will inform Forest Global Drug Safety of all SAEs. Forest Global Drug Safety will be notified immediately regarding any SAE that occurs after informed consent is obtained.

The Principal Investigator will report the event within 24 hours of first knowledge of any AE that meets one of the criteria for an SAE, to Forest Global Drug Safety on an SAE report form. If, during follow-up, any nonserious AE worsens and eventually meets the criteria for an SAE, that AE will be recorded as a new SAE.

The study center will transmit the SAE report form to the SAE [contact]** within 24 hours of first awareness of the event at the study center.

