- Hematologic: Agranulocytosis (rare), Hemolytic anemia (rare)
- Hepatic: Hepatic encephalopathy (rare), Hepatic necrosis (rare), Liver failure (rare)
- Immunologic: Anaphylaxis (rare)
- Musculoskeletal: Fracture of bone (rare), Hip fracture (rare), Rhabdomyolysis (rare)
- Renal: Interstitial nephritis (rare), acute (rare)

Blood Sampling

When blood is drawn from the vein, there may be some temporary discomfort and a slight risk of local pain, bruising, swelling, or blockage of the vein. Rarely, fainting or nerve damage may occur.

B6. RECRUITMENT AND CONSENT PROCEDURES

Recruitment

Potential subjects will be identified in several ways. Some may be found through OMR review of patients seen at the Celiac Center. Patients may be approached by a co-investigator in clinic. Our CCI approved research databases (2007-P-000283 and 2010-P-000006) will be examined for likely candidates. These will be sent a recruitment letter or email or contacted by phone. This study may also be advertised through local celiac support groups such as the Healthy Villi. It is expected that the only subjects for the established celiac disease group will be contacted by mail, email or through ads. And advertisement will also be placed in the Metro.

Participants from prior Celiac-focused studies (2013-P-000035 and 2011-P-000335) will be contacted by phone sent or an email and/or a letter. This email and letter will be identical to the email and letter sent to other prospective participants.

Before contacting patients identified from the medical records or who participated in prior studies, the patient's primary gastroenterologist will be contacted for prior approval.

Consent

Whenever possible, prospective subjects will be sent a copy of the ICF to review in advance of the screening visit. They will have the opportunity to read the ICF and ask any questions they have before they decide to schedule the screening visit. At the screening visit, before any research activities take place, an investigator will review the entire ICF with the subject. The subject will be completely informed verbally of the study procedures, risks and requirements. The subject will be

PI Revision Date: 08Aug2017

given the opportunity to read the ICF. A physician will be available to answer any questions that the subject has. If the subject chooses to enter the study, an MD co-investigator will obtain written informed consent from the subject as well as sign the consent form at that time.

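### The SAE definition stops at five outcomes, so some risks that B5 lists as Serious/Rare can escape 24-hour reporting and the SAE count

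*Combined protocol and SAP*

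**What the plan says.** The SAE definition is in B3.A, Safety Evaluations. It opens: "Serious adverse events (SAEs) will be defined as those that: result in death; are an immediate threat to life; require inpatient hospitalization". The hospitalization item reads in full "require inpatient hospitalization, or prolongation of existing hospitalization", and the list closes with events that "result in persistent or significant disability/incapacity; and/or are a congenital anomaly or birth defect". Nothing follows that refers to medical judgement or medical importance, and no list of events of special interest appears in the visible text.

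The reporting duty is tied to that list: "The Principal Investigator will report the event within 24 hours of first knowledge of any AE that meets one of the criteria for an SAE", using an SAE report form sent to the drug safety department. A non-serious event that worsens is recorded as a new SAE once it satisfies the same criteria. Pregnancy has its own 24-hour report, required even when there is no adverse event.

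B5, Possible Risks, gives a Serious/Rare list for each of the two drugs. For Viokace the gastrointestinal line is "Gastrointestinal: Distal intestinal obstruction syndrome, Fibrosing colonopathy (Rare), Stricture of colon (Rare" and an adjoining line reads "Other: Recurrent tumor, Carcinoma". For omeprazole, which B3.A counts as part of study treatment, one line is "Hematologic: Agranulocytosis (rare), Hemolytic anemia (rare".

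**The concern.** B5 singles out certain harms of the study treatment as serious or rare. The reporting rule in B3.A never refers to those harms. It looks only at what happens to the participant, and its list is closed. An investigator who follows it literally has no ground for classing an event as serious because it is medically important.

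Two things are at stake. One is speed: Safety Evaluations sets no timeline for sending a non-serious adverse event to the drug safety department, so an event outside the five outcomes has no expedited path there. The other is the summary of safety: the same event would not appear in the trial's SAE count.

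**Working it through.** No arithmetic decides this point; it is settled by comparing the two sections.

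**1. Count the criteria in B3.A.** They are (i) death, (ii) immediate danger to life, (iii) admission or a longer stay, (iv) lasting or significant disability, and (v) congenital anomaly. That is five, with hospitalization and its prolongation counted as one. All five describe an outcome, and none names a diagnosis or leaves room for judgement. The only text removed from this part of the section is a contact detail, so the gap is not a redaction.

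**2. Look for another expedited route.** The trigger is "within 24 hours of first knowledge of any AE that meets one of the criteria for an SAE". The upgrade rule for worsening events uses the same criteria, so it does not widen them. The remaining 24-hour route is for pregnancy and does not cover these events.

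**3. Set the B5 examples against the five criteria.**

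| Event in B5 | Drug | Meets a criterion by diagnosis alone? | When it would qualify |
|---|---|---|---|
| Stricture of colon | Viokace | No | If the case brings admission, immediate danger to life, significant disability or death |
| Fibrosing colonopathy | Viokace | No | Same |
| Agranulocytosis | Omeprazole | No | Same |

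**4. Check that the gap can occur in this trial.** Participants are outpatients. B3.A, Laboratory Assessments, schedules the complete blood count at Visit 1 and again at Visit 3, the study conclusion. A haematological abnormality could therefore first appear in someone who is at home, not in immediate danger and not disabled. Under B3.A as written that event is non-serious, and the 24-hour report is not triggered.

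**5. Establish what is retained.** Adverse events are assessed at every visit and contact, contacts take place every 3 (±1) days, and every adverse event receives a causality assessment. The event is captured. What it can lose is SAE classification and expedited transmission.

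**6. Size.** Enrolment is capped at 40. Exposure to active enzyme is at most 40 × 10 = 400 participant-days, and exposure to study omeprazole at most 40 × 34 = 1,360 participant-days. B5 tags all three examples as rare and gives no incidence for any of them, so an expected number of cases cannot be calculated from the documents.

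**The case against.** The strongest case on the other side is that B5 and B3.A do different jobs. B5 discloses product risks; B3.A classifies individual events by outcome. The two can coexist without contradiction, and the whole matter concerns rare events in a short pilot with no bearing on the endpoints.

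Much of that stands, and it rules out several stronger readings that a reader might infer:

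- *That the protocol calls every one of these risks serious and then contradicts itself.* The heading is Serious/Rare, and the three examples carry a rare tag, so they may be listed for rarity. Recurrent tumor and carcinoma sit on a separate line labelled Other. Placing them under the same heading is the natural reading but not a certain one, so the point does not rely on them.
- *That any such event escapes if the participant is not admitted.* Admission is one criterion of five. A case treated without admission is still reportable within 24 hours if it is an immediate danger to life or significantly disabling, and a given case of agranulocytosis might be judged so. The text supports only that such a case can escape.
- *That the events would be lost.* They would be recorded as adverse events with a causality judgement, and upgraded if they later met a criterion.
- *That the SAE report is the only 24-hour route of any kind.* Pregnancy has one too. The accurate statement is that adverse events have no other expedited route.
- *That every event listed in B5 should be an SAE.* That would put a mild hypersensitivity reaction or a slightly low magnesium beside deaths and admissions, and would blur the SAE count.

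The objection does not remove the core of the point. The list is closed, it contains no judgement criterion, and both the 24-hour report and the upgrade rule depend on it. This is a stated rule that can misclassify an event, rather than a detail left unstated.

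**Conclusion.** The point holds in limited form. Under B3.A as written, a case of colon stricture, fibrosing colonopathy or agranulocytosis that is managed without admission, and is neither immediately life-threatening nor significantly disabling, can be classed as non-serious. It would then miss the 24-hour report and the SAE count.

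The practical likelihood is low, and the consequence is delayed transmission and a lower SAE classification, with the event itself still on record. Efficacy endpoints and their analysis are not affected.

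The conclusion rests on two assumptions: that sites apply the definition literally, and that no separate safety document outside the visible text adds a further criterion. It is worth correcting because the rule governs safety reporting and the correction is small.

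**What to change.** Add a sixth criterion to the SAE definition in B3.A, Safety Evaluations: *any other event that the investigator judges medically important*, subject to the same 24-hour report. Reconcile that section with B5 by adding a sentence saying that events listed there as Serious/Rare, for Viokace or omeprazole, are to be assessed against this criterion whether or not the participant is admitted. State also that being listed does not by itself make an event an SAE. Make the matching change on the adverse event form.

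The cost is a sentence or two in the protocol and one item on the form. The downside is an occasional extra expedited report.
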